9.4 STATISTICAL ANALYSES

9.4.1 General Approach

First, we will test the distribution pattern of our data (normal vs non-normal). Continuous data will be presented as means (standard deviations) in case of normal distribution and as medians (ranges) for non-normal distributions. Categorical data will be presented as percentages. Parametric or non-parametric statistical tests will be used based on the distribution of the data (normal, non-normal). In case which it is clinically meaningful, we will transform continuous data into categorical data by creating clinically meaningful categories of the continuous data.

Criteria for statistical significance will be set at alpha of 0.05 (two-tailed tests). Potential covariates that will be considered in the statistical analyses are age, sex, ethnicity, BMI, waist circumference, TGs, glucose levels, HDL levels, Blood Pressure levels, baseline cognitive status.

9.4.2 Analysis of the Primary Endpoints

The primary endpoint will be continuous and will be presented as mean (standard deviation). It will be measured as MRS BHB concentration normalized to Creatine (BHB/Creatine ratio) in bilateral precuneus. For the primary endpoint, repeated-measures mixed models analysis will be performed to examine the effects of the between-subjects factor “Group” (KE drink vs. Placebo group), the within-subjects factor “Time” and their Interaction, separately for acute and chronic effects (Baseline vs. Outcome). Exploratory analyses will include age, sex, weight/BMI, waist circumference, TGs, glucose levels, HDL levels, Blood Pressure levels (reflecting severity of MetS), cognitive status, peripheral ketone levels and EV biomarkers, entered as covariates in the mixed model. If a covariate is not substantively related to the model ($p > 0.15$), it will be dropped.

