6.3 MEASURES TO MINIMIZE BIAS: RANDOMIZATION AND BLINDING

This study will be a double-blinded randomized controlled placebo trial.

To avoid selection bias, eligible participants will be randomly allocated in 1:1 ratio, to either oral intake of KE drink or Placebo, using a computer based random sequence generation method which will be concealed. Randomization will be stratified by age. There will be 2 groups defined as participants age 55-64 and participants ≥ 65 years old. The formulation of KE drinks and Placebo will be done in a way that does not allow participants to find out in which group they are assigned to. Efforts to match the Placebo with KE drinks are described in 6.2.3.

Unintentional break of the blinding of participants will be reported to the IRB as a study deviation.

Credibility expectancy questionnaire (CEQ):

To assess subjects expectations and confirm their blind status, we modified the CEQ, a tool commonly used in studies of chronic pain and anxiety syndromes [54-56](#). The CEQ will be administered on Visits 3 and 4 (i.e., while participants are receiving the study supplement). It has been shown that expectations can alter the outcome of a therapy in diverse populations and conditions, such as Vietnam veterans, social phobia and generalized anxiety disorder; thus, the CEQ is a valuable questionnaire to exclude that any therapy outcomes are explained by expectations. In our study, participants do not have a disease or cognitive impairment. Nevertheless, cognitive performance, an important exploratory outcome, will be assessed and it is conceivable that it may be affected by expectations. Therefore, responses will be compared between groups and may be used as covariate in sensitivity analyses for cognitive outcomes.

The questions that will be asked are:

- “At this point, how effective do you think the supplement you are receiving will be in changing your brain chemistry and improving your cognitive function”
- “How confident would you be in recommending the supplement to a friend who wishes to change her/his brain chemistry and improve her/his cognitive function”
- “By the end of the 28-day period, how much change in your brain chemistry and improvement in your cognitive function do you think will occur”?
- “At this point, how much do you really feel that the supplement you are receiving will help you to change your brain chemistry and improve your cognitive function”

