7.2 PARTICIPANT DISCONTINUATION/WITHDRAWAL FROM THE STUDY

Participants are free to withdraw from participation in the study at any time upon request.

The PI may discontinue a participant from the study for the following reasons:

- Screen failure.
- The participant meets an exclusion criterion (either newly developed or not previously recognized) that precludes further study participation
- The participant has an adverse event (AE), including clinical signs and/or symptoms, laboratory abnormality, or other medical condition or situation, such that continued participation in the study would not be in the best interest of the participant, at the judgment of the PI.
- The participant manifests significant study non-compliance (e.g. the participant was deemed eligible but didn't show for any Visit. Also, if the participant's log of supplement intake during Visit 3 shows multiple skipped doses or skipped days of intervention).
- The participant has any condition, which in the opinion of the PI, could interfere with the study procedures.
- MRI will be stopped at the request of the participant as a result of claustrophobia or problems associated with lying in the scanner for any length of time. If MRS measures for BHB (primary outcome) cannot be obtained, this will constitute discontinuation of the participation.
- Death.

Participants that are discontinued/withdrawn from the study will be replaced by new participants. The reason for participant discontinuation or withdrawal from the study will be recorded on the medical record.

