9.2 SAMPLE SIZE DETERMINATION

The sample size in this study ($n = 50$ for complete data, 25 receiving KE drinks and 25 receiving placebo) gives the ability to detect an effect size (d) of 0.80 at a two-tailed Alpha of 0.05 and a Power of .80. In other concurrent studies, our ketone-sensitive PRESS sequence is capable of detecting an effect size (d) 0.72, roughly equivalent to an 18% change in BHB to creatine ratio. Since we know that brain ketone uptake is proportional to plasma ketones [15](#), we expect that brain BHB levels will change comparably to plasma BHB levels. A prior study using plasma measurements following KE administration versus placebo showed an effect size (d) of 4.05 [32](#), suggesting more than adequate power for detecting brain BHB changes.

Also, in a previous study (Evans et al) [72](#), 8 healthy young male athletes were tested on a domain of cognitive performance (executive function) before and after a period during which they were taking a ketone supplement (similar but not identical to the KE of the present study) while exercising [72](#). This intervention resulted in peripheral BHB of ~ 1.5 to 2.6 mM (less than the level of peripheral BHB elevation we expect with the KE) and showed a significantly better executive function performance, with an effect size (d) of 0.7 [72](#). Since in our proposed study we expect to achieve a greater peripheral BHB induction and our sample size is much greater than Evans et al [72](#), it is likely that our study is powered well enough to detect cognitive changes.

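### The primary Group x Time test compares raw changes without adjusting for the baseline scan, giving up precision by an amount the documents do not let one fix

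*Protocol*

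**What the plan says.** Protocol section 9.4.2, repeated in the SAP under Analysis of the Primary Endpoints, takes BHB/creatine in the precuneus as the endpoint. It says that "repeated-measures mixed models analysis will be performed to examine the effects of the between-subjects factor" Group and the within-subject factor Time, "and their Interaction, separately for acute and chronic effects (Baseline vs. Outcome"). Each model therefore has two time points. The covariates listed there are demographic, metabolic, cognitive, peripheral ketone and EV variables, entered in exploratory analyses. Baseline BHB/creatine is not among them, nor among the potential covariates in section 9.4.1, and no common baseline mean for the arms is stated.

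Section 9.2 and the SAP's sample size section plan for 50 completers, 25 in each arm, and claim that this number "gives the ability to detect an effect size (d) of 0.80 at a two-tailed Alpha of 0.05", with 80% power. They do not say which SD d is divided by, and they give no correlation between scans.

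Section 8.2.3 has two brain scans at each of Visits 2 and 4, one fasting and one after the supplement. Section 9.4.2 does not say which Visit 4 scan is the chronic outcome.

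**The concern.** With two time points, complete data and baseline means free to differ by arm, the Group x Time coefficient is the between-arm difference in mean raw change. Its variance carries the noise of both scans in full. A baseline-adjusted analysis uses the baseline scan only as far as it predicts the outcome, so apart from one degree of freedom it is never less precise in a randomised comparison. With equal SDs at the two scans and r below 0.5, the raw change is even less precise than the outcome scan alone.

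The sample size formula contains no repeated-measures term, so the 80% is not tied to the test that will be run. This is the only primary endpoint in a trial of 50 completers, and the baseline scan is already collected.

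**Working it through.** **Inputs from the documents.** Two-sided alpha 0.05, power 0.80, d = 0.80 and 25 per arm (section 9.2); 1:1 allocation (section 6.3). Withdrawals are replaced (section 7.2), so 25 completers per arm are used.

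**Inputs not in the documents (assumptions, shown as ranges).** The SD basis of d; r, the correlation between the baseline and outcome scans; k = baseline SD / outcome SD.

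**Step 1: the plan's own figure.** For a two-group comparison of means, the normal formula with d = 0.80 gives 25 per arm and power 0.807. The noncentral t with 48 df gives 0.791. The stated figure reproduces, with no correlation needed.

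**Step 2: the planned test.** On simulated two-time-point data, the mixed-model interaction and the t-test on changes gave the same estimates and, to rounding, the same t values (for example 3.752 from both).

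**Step 3: variances, with the outcome SD set to 1.**
- Change score: 1 + k² − 2rk, which is 2(1 − r) when k = 1.
- Baseline-adjusted: 1 − r², whatever k is.
- The first minus the second is (k − r)², which is never negative.

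Effective d is 0.80 divided by the square root of the variance. Power is from the noncentral t with 25 per arm, 48 df for the change score and 47 df for the adjusted analysis (an approximation that ignores chance baseline imbalance).

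**Step 4: d per single-scan (outcome) SD.**

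| k | r | Change variance | Effective d, change | Power, interaction | Effective d, adjusted | Power, adjusted |
|---|---|---|---|---|---|---|
| 1 | 0.2 | 1.60 | 0.632 | 59% | 0.816 | 81% |
| 1 | 0.3 | 1.40 | 0.676 | 65% | 0.839 | 83% |
| 1 | 0.5 | 1.00 | 0.800 | 79% | 0.924 | 89% |
| 1 | 0.7 | 0.60 | 1.033 | 95% | 1.120 | 97% |
| 0.5 | 0.2 | 1.05 | 0.781 | 77% | 0.816 | 81% |
| 0.5 | 0.3 | 0.95 | 0.821 | 81% | 0.839 | 83% |
| 0.5 | 0.5 | 0.75 | 0.924 | 89% | 0.924 | 89% |

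With k = 1, the interaction reaches 80% at r = 0.51 and exceeds it above that. Simulation of the change-score test with k = 1 (20,000 runs) gave 0.590, 0.643 and 0.790 at r = 0.2, 0.3 and 0.5.

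**Step 5: d per change SD, equal SDs.** The interaction has the planned 79% at any r. The adjusted analysis has effective d = 0.80 × sqrt(2/(1 + r)): 1.033 at r = 0.2 (95%), 0.924 at r = 0.5 (89%) and 0.868 at r = 0.7 (85%).

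**The case against.** A reader might infer that the trial is underpowered, at 59–65% for its primary test, or that the stated power holds only at a correlation near 0.5. The documents support neither. Four points on the other side stand:

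- **SD basis.** The primary objective is worded as a change, so reading d per change SD is at least as natural. On that reading the stated power holds at any r.
- **Equal SDs.** The 59% and 65% need k = 1. A fasting scan and a post-dose scan need not have the same spread, and at k = 0.5 most of the gap closes.
- **Correlation.** Values of 0.2–0.3 are assumptions. A low r is plausible if fasting Visit 2 is compared with post-dose Visit 4, but that argument falls away if the fasting Visit 4 scan is the outcome. Above about 0.5, power exceeds 80% even with equal SDs.
- **Effect size.** Section 9.2 offers d = 0.80 as what the sample can detect, not as the expected effect. It expects brain BHB to follow plasma, where it cites d = 4.05. Even with k = 1 and r = 0.2, interaction power is 91% at d = 1.2 and 98% at d = 1.5. Against this, 4.05 is a plasma figure. The MRS figure in the same section is 0.72, at which (per single-scan SD, k = 1) the interaction has about 50–56% at r = 0.2–0.3, against 72–74% with adjustment.

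The interaction is also a valid, unbiased test in a randomised trial and fits a hypothesis framed against both baseline and placebo. None of this favours leaving the baseline unadjusted: adjustment matched or beat the raw change in every scenario computed.

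**Conclusion.** The point holds as one of efficiency and incomplete specification. As written, the primary interaction test compares raw changes, and the power statement belongs to a plain two-group comparison whose SD is not defined.

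With d = 0.80, the cost in power runs from 22 percentage points (single-scan SD, equal SDs, r = 0.2: 59% against 81%) to none (k = 0.5, r = 0.5). On the change-SD reading the planned power is kept, and what is forgone is extra power: 79% against 85–95% for r from 0.7 down to 0.2. Which case applies depends on three quantities the documents do not give, so no shortfall against 80% is shown. If the brain effect is very large, the loss would not matter. The case for adjusting does not depend on settling these unknowns.

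**What to change.** In section 9.4.2 and the SAP, make the primary chronic-effect model baseline-adjusted in one of two ways:

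- a mixed model with the arms constrained to a common Visit 2 fasting (pre-dose) mean, keeping Time and Group x Time and dropping the Group main effect; or
- ANCOVA of the Visit 4 BHB/creatine outcome scan on arm, with Visit 2 fasting BHB/creatine as covariate.

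Randomisation justifies the common mean. Choose one in advance: the two agree only approximately, and they differ when Visit 4 data are missing, which the modified intention-to-treat set allows. Name the single treatment coefficient as the primary test, and name which Visit 4 scan is the outcome. Within-arm change can still be reported alongside.

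In section 9.2 and the SAP, state whether d is per single-scan SD or per change SD, and give the assumed r and SD ratio if the calculation relies on them.

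The cost is wording in the two documents and one degree of freedom for ANCOVA. No further scan or participant is needed.

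### Randomisation is stratified by age group, but the primary model leaves the stratum out and nothing exempts age from the p > 0.15 deletion rule: a modest efficiency and pre-specification gap

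*Protocol*

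**What the plan says.** Protocol 6.3 states that "eligible participants will be randomly allocated in 1:1 ratio", "using a computer based random sequence generation method which will be concealed". It adds that "Randomization will be stratified by age" and that "There will be 2 groups defined as participants age 55-64 and participants" aged 65 or over. Section 4.1 repeats the stratification. Neither section says how balance is kept within each stratum, for example by permuted blocks.

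Protocol 9.4.2 gives the primary analysis as a repeated-measures mixed model with Group, Time and Group x Time, fitted separately for acute and chronic effects. Age follows in the next sentence: "Exploratory analyses will include age, sex, weight/BMI, waist circumference", with further covariates listed after it. The rule after that begins "If a covariate is not substantively related to the model" and drops any covariate with p > 0.15. The stratification factor is not exempted. The SAP section on the primary endpoint has the same content.

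Three other places mention age or added covariates:
- Protocol 9.4.1 and the SAP's general approach list age among potential covariates to be considered, without tying it to a model.
- Protocol 9.4.9 and its SAP counterpart call added covariates for the primary endpoint exploratory.
- Protocol 9.4.7 and its SAP counterpart allow, but do not require, exploratory subgroup analyses by age group.

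No section commits the age stratum to the primary model.

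**The concern.** The sponsor judged age important enough to constrain the allocation, and the analysis does not carry that choice through. When arms are balanced within strata, differences between strata cannot contribute to the treatment contrast. An analysis without the stratum still counts that between-stratum variance as noise. The standard error is then larger than the real sampling error, the test is conservative and the confidence interval is wider than the design supports.

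The p > 0.15 rule is a separate problem. It lets a data-dependent screen in about 50 people decide whether a design factor stays in the model. A factor fixed by the randomisation should be kept or left out in advance.

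**Working it through.** **Inputs from the documents.** Protocol 9.2: n = 50 "for complete data, 25 receiving KE drinks and 25 receiving placebo", which "gives the ability to detect an effect size (d) of 0.80 at a two-tailed Alpha of 0.05 and a Power of .80". Two age strata and 1:1 allocation (6.3). Model terms from 9.4.2.

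**Assumptions not in the documents.** The strata are of equal size. R2 is the share of the within-arm variance of the change in BHB/creatine that the stratum explains, varied from 0 to 0.20. d = 0.80 is read on the SD of the change.

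**Step 1: the plan's own figure.** The SE of the difference on the d scale is sqrt(2/25) = 0.283, so the standardised effect is 0.80/0.283 = 2.83. Power is 0.807 by the normal approximation and 0.791 by the exact t test with 48 df. Both reproduce the stated 0.80.

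**Step 2: which term matters.** With two time points and complete data, Group x Time is the between-arm difference in mean change. A stable age difference in BHB/creatine level cancels within each person. Two-time random-intercept models fitted to 40 simulated data sets confirm this: the mean SE of Group x Time was 0.2769 both without a stratum term and with a stratum main effect. Only stratum x Time can change the treatment test, and R2 must therefore refer to the change.

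**Step 3: power with the stratum in the model.** The residual SD falls by the factor sqrt(1 - R2), so the effective d is 0.80/sqrt(1 - R2), tested with 47 df. At R2 = 0.10 this is 0.80/0.949 = 0.843, and exact-t power is 0.832.

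**Step 4: type I error without the stratum, allocation balanced within strata.** The model SE stays near 0.283, but the estimate varies with SD of about 0.283 x sqrt(1 - R2). The critical value 2.011 therefore acts like 2.011/sqrt(1 - R2). At R2 = 0.05, 0.10 and 0.20 that is 2.063, 2.119 and 2.248, with two-sided t tail areas of 0.045, 0.039 and 0.029.

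**Step 5: simulation of the change score.** 20,000 trials per scenario, arms balanced within strata to within one person, with the odd person's arm chosen at random:

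| R2 of change | Type I, stratum omitted | Type I, included | Power, omitted | Power, included |
|---|---|---|---|---|
| 0 | 0.051 | 0.051 | 0.793 | 0.793 |
| 0.02 | 0.047 | 0.049 | 0.793 | 0.798 |
| 0.05 | 0.045 | 0.052 | 0.796 | 0.812 |
| 0.10 | 0.036 | 0.046 | 0.804 | 0.833 |
| 0.20 | 0.030 | 0.050 | 0.813 | 0.872 |

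A separate run of 60,000 trials gave type I errors of 0.0448, 0.0398 and 0.0300 at R2 = 0.05, 0.10 and 0.20 with the stratum omitted. These agree with step 4, so the 0.036 in the table is simulation noise around 0.04. At R2 = 0.10 the model SE without the stratum averages 0.282 against a true SD of 0.267.

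**Step 6: unrestricted allocation (a coin flip per participant).** With the stratum omitted, type I error at R2 = 0.10 is 0.053, which is nominal. Power is 0.779 omitted and 0.811 included. The error bars are then honest, but power is still lost.

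**The case against.** **Nothing shows that age predicts the change.** This stands. If the effect of age is only on level, or R2 is near zero, the omission costs nothing: power is 0.79 either way at R2 = 0, and inclusion adds about half a point at R2 = 0.02.

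**The conservative test needs balance within strata, which is not stated.** This also stands. A reader might infer that omitting a stratification factor always makes the test run below 5%. The documents do not support that, because 6.3 says stratified but describes no blocks or other restriction, and step 6 shows a nominal error rate without one.

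**The power gain is easy to overstate.** A reader might set the adjusted powers of 0.81, 0.83 and 0.87 against about 0.78 unadjusted. That baseline appears only if a one-person imbalance is fixed in the same unfavourable direction in every simulated trial. The mirrored layout gives about 0.82, 0.83 and 0.85. With the direction random, the unadjusted power is 0.80, 0.80 and 0.81, and the gain is about 2, 3 and 6 points.

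**Stratification still does its job.** It is tempting to say its benefit is thrown away. It still protects against chance age imbalance between arms, whichever model is fitted. What is lost is precision and the matching standard error.

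**Age is not confined to exploratory models.** It is also a potential covariate in 9.4.1 and the SAP's general approach. That is correct, but it commits no model to it.

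**The sponsor expects far larger effects.** Protocol 9.2 cites a plasma d of 4.05. If brain effects come anywhere near that, a few points of power at d = 0.80 will not change the conclusion. This limits the practical weight of the point, but the trial is justified at d = 0.80, where exact-t power is 0.791.

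**Conclusion.** The omission is plain in both documents: the randomisation stratum is not in the primary model, and age as a covariate can be deleted on its p-value. The consequence is modest and conditional. Power is lost only if the age stratum predicts the change in BHB/creatine: about 2, 3 and 6 points at assumed R2 of 0.05, 0.10 and 0.20, and none at zero. The conservative test, at about 4.5%, 4.0% and 3.0% for the same R2, also requires balanced allocation within strata.

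The point should not be read as a false-positive risk, a bias or a wrong sample size. The error is on the conservative side, and the planned power of 0.80 is approximately met without adjustment (0.79 by exact t). It is an efficiency and pre-specification gap, worth closing because the change is nearly free. The figures rest on equal strata, complete data and d defined on the change.

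**What to change.** In Protocol 9.4.2 and the matching SAP section:
- Include the randomisation stratum (55-64, 65 and over) and stratum x Time as fixed effects in the primary model. A main effect alone does not alter the Group x Time test.
- Keep both terms whatever their p-values, and exempt them from the p > 0.15 rule.
- Do the same in the secondary and exploratory outcome models.

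In Protocol 6.3, state how allocation is restricted within strata, or that it is not. If block sizes should stay unknown to site staff, the sponsor can hold that detail in a restricted document.

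The cost is a sentence or two in each document and about one degree of freedom for the treatment test (48 to 47). If age is unrelated to the change and arms are balanced within strata, power is 0.79 with or without the terms. Under coin-flip allocation the cost is slightly higher. The expected squared chance correlation between arm and stratum is 1/49, about 2% of the variance, which lowers power from about 0.79 to about 0.78.

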implies that the ability of a ketogenic intervention to provide ketones to the brain is directly analogous to its ability to raise ketone levels in the periphery. The cerebral metabolic rate (CMR) of ketone bodies (AcAc and BHB) can be quantified with the use of PET scans using ketone tracers, whereas their concentration in the brain tissue *in vivo* may be quantified by Magnetic Resonance Spectroscopy (MRS) [4,19,34](#). Although a head to head comparison of brain ketone metabolism assessed by PET and brain ketone concentration by MRS quantification has not been reported in the literature, their association is likely given that they both correlate closely with peripheral levels. Therefore, pharmacodynamic effects of oral KE supplementation could be assessed in a study, in which peripheral ketone levels are measured in plasma and brain ketone levels are measured by MRS. The proposed study intends to measure both and examine their associations with biomarkers of neuronal metabolism and cognition.

[figure not shown]
[figure not shown]

Figure 4. Data collated from multiple studies reveal the direct, linear relation between plasma ketone concentration and brain ketone uptake in: AD and healthy age-matched controls (beige and orange circles), postprandial state (yellow boxes), AD and healthy adults from a second study (light and dark green triangles), AD and healthy adults from a third study (light and dark blue rhombuses), BHB infusion (gray triangles), 40-day fast (black triangles), 60-day fast (white box); CMR: Cerebral Metabolic Rate; Two relationships are shown, one for plasma BHB vs rate of brain BHB uptake (solid line, $R^2 = 0.97$; $Y = 1.57X - 0.20$; $P < 0.0001$) and one for plasma AcAc vs rate of brain AcAc uptake (dotted line, $R^2 = 0.83$; $Y = 3.46X - 0.03$; $P < 0.0001$)^{[30](#)}

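### Ketone and EV covariates in the exploratory brain-BHB models are not limited to pre-dose values, and the expectancy score exists only on treatment; time-varying entry could remove part or all of the KE effect

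*Protocol*

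**What the plan says.** The primary analysis is a repeated-measures mixed model of the BHB/creatine ratio with Group, Time and their interaction, run separately for acute and chronic effects (Protocol 9.4.2; SAP, Analysis of the Primary Endpoints). Both documents then plan exploratory versions with a longer list of variables, ending in "cognitive status, peripheral ketone levels and EV biomarkers, entered as covariates in the mixed model". A covariate with p > 0.15 is dropped. Neither document gives the visit or time of measurement for the ketone and EV values.

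Both variables are measured before and during treatment. Under the Schedule of Activities (1.3), serum BHB is taken fasting and about 60 minutes after the dose at Visits 2, 3 and 4. EV blood is drawn only before the dose at each of those visits.

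The protocol treats both as responding to the supplement. The Figure 4 legend in 2.2.5 describes "the direct, linear relation between plasma ketone concentration and brain ketone uptake". Section 9.2 expects brain BHB to follow plasma BHB and cites a plasma effect of d = 4.05. The objectives table in Section 3 expects EV biomarkers to move with brain BHB, serum BHB and cognition.

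On expectancy, Protocol 6.3 says "The CEQ will be administered on Visits 3 and 4", while participants are taking the supplement, and that responses "may be used as covariate in sensitivity analyses for cognitive outcomes". Protocol 9.4.7 and the SAP's Sub-Group Analyses repeat the option as exploratory.

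**The concern.** A covariate that lies between treatment and outcome changes the question being asked. If on-treatment plasma BHB sits in the model beside Group and Time, the Group x Time term estimates only the part of the KE effect that does not pass through plasma ketones. On the protocol's own reasoning that part may be small. EV biomarkers raise the same problem in the 28-day comparison. In the acute Visit 2 comparison, the only EV sample is the pre-dose one, so it is a baseline value.

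The p > 0.15 rule adds to the difficulty, because it is likeliest to keep a covariate when that covariate carries more of the effect.

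The CEQ has no pre-dose score, so any adjustment for it is post-randomisation. Its items ask how much improvement participants feel will occur. A benefit already noticed by Visit 3 can raise the score, and adjusting for it may then take out real effect. Section 6.3 wants the CEQ to rule out expectation as the explanation of an outcome. This adjustment cannot show that, in either direction.

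What is at stake is the reading of the exploratory adjusted estimates in a small proof-of-concept trial meant to inform a possible trial in Alzheimer's disease. The primary test itself is not at stake.

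**Working it through.** **1. The plan's own figure.** Inputs from Protocol 9.2: "25 receiving KE drinks and 25 receiving placebo", which "gives the ability to detect an effect size (d) of 0.80 at a two-tailed Alpha of 0.05 and a Power of .80". Allocation is 1:1 (6.3).

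n per arm = 2(1.960 + 0.842)² / 0.80² = 2 × 7.85 / 0.64 = 24.5, so 25. Power at 25 per arm is 0.807 by the normal approximation and 0.791 by the noncentral t. The stated design reproduces.

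**2. Collinearity alone.** With equal arms separated by d on the covariate, the share of covariate variance explained by arm is d²/(d² + 4). For d = 4.05 this is 16.40/20.40 = 0.804. The variance inflation is 1/(1 − 0.804) = 5.10, and the standard error grows by √5.10 = 2.26.

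**3. Change-score simulation.** Settings: 25 per arm, total effect 0.80 SD, 4,000 runs per cell. The outcome is regressed on Group with and without an on-treatment covariate that treatment shifts by dM standard deviations. The mediated share is an assumption, because the documents give none, so the full range is shown. dM = 4.05 is the protocol's plasma figure; dM = 1.0 is assumed, for a covariate that responds much less.

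| Share mediated | dM = 4.05: effect | significant | dM = 1.0: effect | significant |
|---|---|---|---|---|
| 0% | 0.80 | 22% | 0.80 | 69% |
| 25% | 0.61 | 16% | 0.60 | 47% |
| 50% | 0.39 | 9% | 0.40 | 26% |
| 75% | 0.19 | 6% | 0.20 | 12% |
| 100% | −0.02 | 5% | 0.00 | 5% |

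Without the covariate, the effect is about 0.80 and is significant in about 79% of runs in every row. With a baseline covariate instead (assumed correlation 0.3 with the outcome), the effect stays at 0.80 and power is 83%.

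**4. Two-visit mixed model, closer to the plan.** Settings: 25 per arm, full mediation, ketone shift 4.05, 80 runs.

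- No covariate: Group x Time 0.77, significant in 80% of runs.
- Time-varying ketones: −0.07, significant in 5%, with the standard error inflated about 1.6-fold. The factor is below 2.26 mainly because the change between two visits carries the noise of both ketone measurements.
- Baseline ketones, or a single post-dose value per person entered as a main effect: Group x Time unchanged. In one complete two-visit data set the estimate was 0.742 with standard error 0.286, with and without the single post-dose value.

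Eighty runs is a small number; the Monte Carlo standard error of the 80% figure is √(0.8 × 0.2/80) = 0.045. The drop from 80% to 5% is far larger than that.

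**5. The p > 0.15 rule.** In the mixed model with full mediation, time-varying ketones were kept in 81% of runs. In the change-score model with dM = 4.05, plasma BHB was kept in 15% of runs with no mediation and about 47% with full mediation. Applying the rule at full mediation in that model gave a mean KE effect of 0.20, significant in 45% of runs.

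**The case against.** The strongest reply is that the plan may mean baseline values. Protocol 9.4.1 says baseline for cognitive status, and 9.4.5 lists nearly the same variables, including ketones and EV levels, among baseline characteristics. Under that reading nothing is lost. This stands: the plan leaves the matter open and does not prescribe adjustment for on-treatment values.

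Even on-treatment values do harm only in some models. A single value per person entered as a main effect leaves Group x Time untouched in complete two-visit data. Ketones and EV markers must enter as time-varying covariates. The CEQ needs a change-score or ANCOVA model, or a covariate-by-time term. This also stands.

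The figure d = 4.05 comes from plasma measured after KE intake. Section 2.3.3 says ketones return to baseline within 4 hours, so fasting values may separate the arms far less. The dM = 1.0 columns show that the standard-error penalty then shrinks, but the attenuation does not.

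A reader might infer more than the documents support:

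- That the primary result is compromised. It is not: the adjusted models are labelled exploratory (Protocol 9.4.2 and 9.4.9; SAP, Exploratory Analyses), and the unadjusted Group x Time test stands apart from them.
- That the effect would be removed outright. That is the 100% row; the documents give no share.
- That an attenuated estimate would be reported as a failed robustness check. Neither document describes the ketone and EV models as one.

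The CEQ adjustment is also optional and confined to cognition, itself exploratory.

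The reply does not remove the need for the change. The text says these analyses will include ketones and EV biomarkers, both have on-treatment values, and measurement time decides whether the estimate means anything. For the CEQ, no baseline reading is possible.

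**Conclusion.** The concern holds in a limited form. The exploratory models of brain BHB are under-specified at a point that can move the estimated KE effect from about 0.8 SD to anywhere down to about 0. Where it falls depends on the mediated share, on whether on-treatment values enter as time-varying covariates, and on whether the drop rule keeps them. Standard errors would rise by about 1.6-fold in a two-visit mixed model, or 2.3-fold in a change-score model, if the covariate separates the arms by d = 4.05. Baseline covariates carry no such cost. For EV biomarkers the concern is confined to the 28-day comparison. CEQ-adjusted cognitive estimates cannot settle whether expectation explains an effect; the size of any distortion cannot be given, because the documents quantify no shift in expectancy.

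The simulations assume complete data in 25 per arm, normal errors and a linear path through a single covariate. The change-score version is a simplification of the planned model.

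**What to change.** In Protocol 9.4.2 and the SAP:

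1. State that covariates in every model reporting a treatment effect are restricted to values measured before the first dose. Visit 2 fasting serum BHB and pre-dose EV levels are already collected.
2. Replace the p > 0.15 drop rule with a fixed, named set of baseline covariates.
3. Report on-treatment ketones, EV biomarkers and CEQ scores only in analyses labelled as association or mediation, with no adjusted treatment claim. This still serves the stated aim of relating brain BHB to peripheral ketones and EV markers.
4. Compare CEQ scores between arms descriptively, and amend Protocol 6.3 and 9.4.7 and the SAP's Sub-Group Analyses to match.

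A pre-dose CEQ is optional and not needed for this fix. It could not assess blinding, and if added mid-trial it would be missing for participants already started.

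The cost is a change of wording and the loss of the exploratory treatment estimates adjusted for on-treatment values. No new data or visits are needed.
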